This analysis plan was written prior to the completion of recruitment and was prepared according to UoS SOPs and guidance documents.

2. Definition of terms/acronyms

AE	Adverse event
CONSORT	Consolidated standards of reporting trials
CMT	Cognitive muscular therapy
NIHR	National Institute of Health Research
CTIMP	Clinical trial of Investigational Medicinal Product
RCT	Randomised controlled trial.
SAE	Serious adverse event
SAP	Statistical analysis plan

3. Design

This study is an open, multi-centred, two-armed feasibility, randomised trial with allocation at the patient level, with embedded health economic and qualitative evaluations (not detailed further in this SAP). The two arms are: cognitive muscular therapy (CMT) and psychologically informed physiotherapy

Full details of the background and design of the trial are presented in the protocol (Protocol-(COMPIN)- v5 (17-04-24).docx)

4. Trial objectives

This trial aims to deliver key parameters that are required to run a future, pragmatic, two-arm RCT.

4.1 Primary objective

This trial aims to gain insight into whether CMT is more effective than PiP for patients with chronic non-specific neck pain.

4.2 Secondary objectives

This trial will examine, and aims to gain insight into, the following secondary objectives:

- Can sufficient numbers of study participants be recruited and retained to enable an RCT? (feasibility trial)
- What is the physiotherapist acceptability of the intervention? (qualitative evaluation)
- What is the patient acceptability of the intervention? (feasibility trial via adherence, and qualitative evaluation)
- What is the suitability of various outcome measures for use in an RCT? (feasibility trial)

The following stop-go criteria will be monitored to indicate overall trial feasibility.

1 Recruitment: Average participants recruited per month: red: <4 per month; amber: 4-6 per month; green> 6 per month.

2: Adherence/retention: Participants attending >5 (of 7) clinical sessions: <60%; amber=60-79%; green \geq 80%.

3: Outcomes: Participants providing 14-week and 6 month data: red<60%; amber=60-79%; green \geq 80%. Appropriateness of outcomes determine via qualitative evaluation.

4 Acceptability to patients. Determined via the qualitative evaluation.

5. Outcomes

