5.3.3 Intervention adherence

The number of participants attending clinical sessions will be monitored at each site throughout the trial. The intervention consists of up to 7 sessions.

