5.3.4 Intervention fidelity

The PiP arm will be monitored for fidelity through the review of clinical notes.

Step 2- Consistency of fidelity check between two raters

- Same set of five notes will be analysed by both raters.
- Following this, the scoring will be compared for consistency, aiming for a cohens kappa score of 0.7 . If above 0.7, ok to continue to step 3. If below 0.7, discussion to clarify areas of inconsistency.
- Following this, an additional set of five notes checked. Consistency scored with cohens kappa. If continues below 0.7, consider change of methods, fidelity assessment structure or processes. Repeat stage 1 and 2. If above 0.7, continue to step 3

Step 3- intra tester reliability

- Same set of five notes analysed again 2 weeks later.

- Intraclass Correlation Coefficient (ICC) calculated. If above 0.75, ok to continue to step 4. If below 0.75. Repeated 1 week later.
- If repeated test below 0.75, review understanding of checklist and processes.
- Repeat 1 week later, if below 0.75, repeat step 1.

Step 4- stratified sampling of participants into red (2 sets) /amber (3 sets) /green participants (4 or 5 sets)

- Participants stratified into red/ amber/ green.
- Once stratified, participants randomly sampled for fidelity assessment using Microsoft excel. Aiming for 4 green= 16-20 notes, 4 amber= 12 notes and 4 red participants= 8 notes. Maximum sets of notes = 40 notes + 10 pilot notes= 50 sets of notes.
- Participants then randomly allocated to rater 1 and rater 2 aiming for even distribution of red/amber/green participants.

Step 5- Assessments analysed

- Descriptive analysis of scores broken down into tester and red/amber/green categories. Mean (SD) scores presented.
- Kappa score for inter tester
- ICC for intra tester

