10.5 Primary analyses

The recruitment rate (defined as the number of recruited participants divided by the number of eligible participants), will be estimated along with a 95% CI. The number of participants recruited will be presented by site, as will the overall average number of participants recruited per site per month.

The trial retention will be measured at the end of the 8-month study follow-up. For each outcome, an estimate of the attrition rate (the number of forms not returned divided by the number of forms due) will be produced along with a 95% confidence interval. This will be done for the study overall and by group (treatment vs control).

Intervention adherence will be measured at the 14 week follow up. Adherence will be expressed as a percentage with a maximum of 100% attendance reflecting 7 out of 7 treatment sessions attended for CMT and 5/5 attended for PiP. The total number and percentage of participants attending >66% of CMT sessions and 100% of PiP F2F sessions.

These summaries will be used to assess success of the trial against the pre-specified progression criteria.

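### The adherence stop-go criterion starts at 6 of 7 sessions in SAP section 4.2 but at 5 of 7 for CMT in section 10.5, and section 4.2 names no arm

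*SAP*

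**What the plan says.** Section 4.2 lists the stop-go criteria. Criterion 2, on adherence and retention, is the proportion of "Participants attending >5 (of 7) clinical sessions", with the bands "<60%; amber=60-79%; green \geq 80"%. No arm is named. The lowest band carries no colour label here; I read it as red, as in criteria 1 and 3.

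Section 5.3.3, on intervention adherence, says "The intervention consists of up to 7 sessions" and again names no arm.

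Section 10.5 expresses adherence as a percentage of each arm's own maximum, with full attendance being "7 out of 7 treatment sessions attended for CMT and 5/5 attended for PiP". It then adds a dichotomised count: "The total number and percentage of participants attending >66% of CMT sessions and 100% of PiP F2F sessions". It closes the adherence, recruitment and retention summaries with: "These summaries will be used to assess success of the trial against the pre-specified progression criteria".

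**The concern.** Section 10.5 is meant to supply the figure that criterion 2 is judged on, but its dichotomised count uses a different cut for the CMT arm from the one in section 4.2. The difference is a single session, and it falls on participants who attend exactly 5.

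Adherence is among the primary feasibility outcomes in section 5.1, and criterion 2 is one of four stop-go criteria. If two definitions stand, the analyst has to choose between them. Section 5.3.3 says attendance is monitored at each site throughout the trial, so that choice could be made with the attendance already known. The unnamed arm in section 4.2 adds a second open question, namely whether PiP participants enter the criterion at all.

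**Working it through.** **Inputs.** Threshold and bands for criterion 2: section 4.2. Session maxima (CMT 7, PiP 5) and the dichotomised rule: section 10.5. Sample size 48, dropout 20%, about 19 per group: section 7.

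**Arm size.** The SAP's own figure reproduces with equal arms: 48 × (1 − 0.20) / 2 = 19.2, stated as approximately 19. The allocation ratio is not stated, so 24 randomised per arm is an inference from this.

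**Which session counts qualify in CMT.** More than 5 of 7 means at least 6. More than 66% of 7 means more than 0.66 × 7 = 4.62, so at least 5.

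| CMT sessions attended | Share of 7 | Meets 4.2 | Meets 10.5 |
|---|---|---|---|
| 4 | 57.1% | no | no |
| 5 | 71.4% | no | yes |
| 6 | 85.7% | yes | yes |
| 7 | 100% | yes | yes |

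Only the row for 5 sessions differs.

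**Effect on the proportion.** Let *a* be the number of CMT participants attending 6 or 7 sessions and *b* the number attending exactly 5, out of 24. Section 4.2 gives *a*/24 and section 10.5 gives (*a* + *b*)/24. The gap is *b*/24, or 1/24 = 4.2 percentage points per participant.

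**Effect on the colour.** Amber needs 0.60 × 24 = 14.4, so 15 participants. Green needs 0.80 × 24 = 19.2, so 20. The colour changes whenever *a* is below one of these counts and *a* + *b* reaches it. A move from red to green needs *a* ≤ 14 and *a* + *b* ≥ 20, so at least 6 participants at exactly 5 sessions. Assumed patterns, since the SAP gives no attendance figures:

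| *a* (6 or 7) | *b* (exactly 5) | Section 4.2 | Section 10.5 |
|---|---|---|---|
| 12 | 8 | 12/24 = 50.0%, red | 20/24 = 83.3%, green |
| 15 | 5 | 15/24 = 62.5%, amber | 20/24 = 83.3%, green |
| 14 | 1 | 14/24 = 58.3%, red | 15/24 = 62.5%, amber |
| 20 | 2 | 20/24 = 83.3%, green | 22/24 = 91.7%, green |
| 20 | 0 | 20/24 = 83.3%, green | 20/24 = 83.3%, green |

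**If criterion 2 were read as covering both arms.** PiP has at most 5 sessions, and 5 is not more than 5, so no PiP participant could qualify. With perfect attendance in both arms the proportion would be 24/48 = 50%. Amber would need 0.60 × 48 = 28.8, so 29 participants. This holds only under that reading and with equal arms.

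**The case against.** The best case for the plan is that criterion 2 was meant for CMT. It says of 7, and by section 10.5 only CMT has 7 sessions. Section 5.3.3 speaks of the intervention having up to 7, and elsewhere the SAP sets intervention against control. The protocol, which was not available for this review, may name the arm. This is the most natural reading, and it stands. A reader might otherwise infer that the criterion is bound to come out red because PiP can never meet it. The SAP does not support that as a finding; it follows only if the unnamed arm is taken to mean both.

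A reader might also infer that the two arms cannot be compared on adherence. That goes too far. Section 10.5 already gives each arm's attendance as a percentage of its own maximum, which is a common scale. Only the dichotomised counts use different cut-offs (more than 66% against 100%), and arm-specific cut-offs may be deliberate.

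Nor does the phrase "green participants (4 or 5 sets") in section 5.3.4 contradict the 100% rule for PiP. Those colours are strata for sampling notes for the fidelity audit, not a standard of adherence.

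The conflict may also turn out harmless. If non-attendance is mostly early dropout, few will attend exactly 5 and the two definitions will agree or nearly so. Modelling attendance session by session would require assuming independence between sessions, which nothing in the SAP supports, so I rely on counts instead.

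Finally, section 4.2 says the criteria are monitored to indicate feasibility and attaches no stated consequence to a single red. It would overstate the matter to say that this item alone decides whether a main trial follows.

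None of this removes the mismatch within CMT.

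**Conclusion.** The point holds for the CMT arm. Section 4.2 requires at least 6 of 7 sessions, section 10.5 at least 5 of 7, and the second is said to feed the criteria set in the first. The gap equals the share of CMT participants attending exactly 5 sessions. It can be zero. One such participant can be enough to change a band, and 8 of 24 can turn 50% (red) into 83% (green).

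The session arithmetic needs no assumption. The percentages assume 24 in CMT, inferred from about 19 per group after 20% dropout, and the attendance patterns are illustrations. The separate omission in section 4.2, that no arm is named, is real but secondary. It matters because a reading over both arms would cap the figure at about 50% with equal allocation.

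**What to change.** Reconcile sections 4.2, 5.3.3 and 10.5, and document the decision before attendance data are examined.

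- Write one numerical CMT threshold in both 4.2 and 10.5: either 6 or more of 7, or 5 or more of 7. The SAP does not settle which was intended, so the sponsor must say.
- State in 4.2 that criterion 2 is assessed in the CMT arm and is not pooled with PiP, and name in 5.3.3 the arm to which the 7 sessions apply.
- Report PiP attendance beside it as a percentage of its own 5 sessions. State any PiP cut-off explicitly as a number of sessions, because a shared percentage does not translate cleanly: 6/7 = 85.7% whereas 4/5 = 80%, so a cut at 85.7% or more means 5 of 5, while one written as more than 5/7 (71.4%) means 4 of 5.
- Add the missing label for the lowest band of criterion 2.

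The cost is wording in three SAP sections. No new data are needed.

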7.2 External datasets

1. Recruitment data will be stored in a recruitment screening log and spreadsheet by the trial research coordinator.
2. Consent data will be stored in a consent log and spreadsheet managed by the trial research coordinator.

7. Sample Size

We plan to recruit 48 participants to the study. Assuming a dropout of 20%, this should provide approximately 19 in each group for the final analysis. The primary objective of this study is to assess the feasibility, and inform planning, of a future large-scale clinical trial. Sample sizes of between 24 and 70 have been recommended for feasibility trials to provide a reliable estimate of parameters required to calculate the sample size for a main trial, e.g. standard deviation of continuous outcomes, recruitment, and attrition rates. Our sample of 48 is therefore in line with these recommendations.

8. Randomisation

Randomisation will be carried out via a web-based randomisation system (<https://www.sealedenvelope.com/>). The allocation sequence will be generated by the lead or co-investigator not otherwise involved in the recruitment/treatment of participants. Once group allocation has been confirmed the intervention coordinator (member of the research team) will liaise with participants over the phone to schedule the appointments.

10. Analysis

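### Stop-go criterion 2 needs 6 or 7 of 7 sessions, but the adherence summary meant to feed it counts CMT participants from 5 sessions upward, and the criterion does not name the arm it covers

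*SAP*

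**What the plan says.** Section 4.2 defines the adherence/retention criterion as the percentage of "Participants attending >5 (of 7) clinical sessions", with bands "<60%; amber=60-79%; green \geq 80"%. The lowest band has no colour label, and I take it as red by analogy with criteria 1 and 3. No arm is named.

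Section 10.5 sets full attendance at "7 out of 7 treatment sessions attended for CMT and 5/5 attended for PiP". It then lists one count: "The total number and percentage of participants attending >66% of CMT sessions and 100% of PiP F2F sessions". It closes with "These summaries will be used to assess success of the trial against the pre-specified progression criteria".

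Section 5.3.3 says "The intervention consists of up to 7 sessions", without separating the arms. The PiP notes audit in section 5.3.4 describes "stratified sampling of participants into red (2 sets) /amber (3 sets) /green participants (4 or 5 sets"), which agrees with a PiP maximum of 5.

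**The concern.** Section 10.5 presents its summaries as the input to the stop-go decision, so its adherence count should be the quantity that criterion 2 asks for. It is not: the two sections classify a CMT participant with exactly 5 sessions in opposite ways.

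Adherence is one of the feasibility outcomes that section 5.1 treats as primary, and one of three numeric stop-go criteria. The trial is open and attendance is monitored at each site throughout. If two counts remain available, the choice between them can be made after attendance is known, which is what a pre-specified threshold should prevent.

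The unnamed arm adds a second uncertainty. A criterion expressed out of 7 cannot be applied as it stands to an arm whose full course is 5.

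**Working it through.** **Inputs.** Criterion 2 and its bands come from section 4.2. The attendance rules and the arm maxima (CMT 7, PiP 5) come from section 10.5. The Sample Size section gives a total of 48, 20% dropout and about 19 per group.

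**The plan's own figure.** 48 × (1 − 0.20) = 38.4, and 38.4 / 2 = 19.2 per group, which matches the stated 19. This implies about 24 randomised per arm. Equal allocation is inferred from this and is not stated.

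**Session counts implied by each rule (CMT).**
- Section 4.2: more than 5 of 7 means at least 6; 6/7 = 85.7%.
- Section 10.5: 0.66 × 7 = 4.62, so at least 5; 5/7 = 71.4%. Reading 66% as two-thirds gives 4.67 and the same answer.

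**Effect on the colour, by simple counts.** Assume 24 in CMT and apply the section 4.2 bands to both counts.
- 14 attend 6 or 7 sessions and 6 attend exactly 5: 14/24 = 58.3% (red) against 20/24 = 83.3% (green).
- 14 attend 6 or 7 and only 1 attends exactly 5: 14/24 = 58.3% (red) against 15/24 = 62.5% (amber).
- 20 attend all 7 and 4 stop before session 5: 20/24 = 83.3% under both (green).

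**Effect on the colour, by a simple model.** Let X be the number of sessions attended, binomial with n = 7 and per-session attendance probability q. Both q and independence between sessions are assumptions. For example, at q = 0.80:
- P(X ≥ 6) = 7 × 0.8⁶ × 0.2 + 0.8⁷ = 0.367 + 0.210 = 0.577
- P(X ≥ 5) = 0.577 + 21 × 0.8⁵ × 0.2² = 0.577 + 0.275 = 0.852

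| q | 6 or more (4.2) | 5 or more (10.5) |
|---|---|---|
| 0.65 | 23.4%, red | 53.2%, red |
| 0.75 | 44.5%, red | 75.6%, amber |
| 0.80 | 57.7%, red | 85.2%, green |
| 0.85 | 71.7%, amber | 92.6%, green |
| 0.90 | 85.0%, green | 97.4%, green |

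**If criterion 2 covered both arms.** No PiP participant can exceed 5, so PiP contributes none. With 24 per arm, the most that can be reached is 24/48 = 50%, below the 60% line. Perfect attendance under the section 10.5 rules would give 48/48 = 100%.

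**The case against.** Three points on the other side deserve weight.

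1. **Only section 4.2 carries colour bands.** Section 10.5 refers back to the pre-specified criteria, so section 4.2 can be read as governing, with the 66% count as an additional summary. A reader might infer that the SAP sets two rival traffic lights; it does not. A green result from the 10.5 count arises only when the 4.2 bands are applied to it. What remains is that 10.5 offers its summaries for the decision and names no count that matches the criterion.

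2. **The criterion probably means CMT only.** It is expressed out of 7, only CMT has 7 sessions, and section 5.3.3 uses the word intervention for the course of up to 7. A reader might infer that criterion 2 must be red even with perfect attendance. That holds only if both arms are pooled, which the denominator argues against. Because the text says participants without restriction, the scope still needs stating. The 6-versus-5 conflict survives a CMT-only reading.

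3. **The size depends on assumptions.** The SAP gives no attendance distribution. If people mostly either finish or drop out early, few will attend exactly 5 and the two counts will nearly agree. This stands: a change of colour is possible, but its likelihood is unknown.

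The sign in section 4.2 might be a slip for at least 5, which would agree with 10.5. The document does not settle that. A slip in the decision rule would still need correcting.

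**Conclusion.** The inconsistency is real and needs no model: CMT participants with exactly 5 sessions do not count under section 4.2 and do count under section 10.5. Whether it changes the colour depends on how many such participants there are. Under the binomial illustration the colours differ at attendance probabilities of 0.75, 0.80 and 0.85, and agree at 0.65 and 0.90. It would therefore be wrong to say that the colour always turns on which section is followed.

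The 50% ceiling is conditional on pooling the arms and on 24 per arm, and pooling is the less natural reading. The firm finding about scope is that the arm and denominator are unstated. No treatment-effect estimate is affected. Because this is a decision threshold on a primary feasibility outcome, it should be settled before it is used.

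**What to change.** Before attendance is summarised for the progression decision:

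- Reconcile sections 4.2 and 10.5 to one count for criterion 2, written in both places as a number of sessions attended. Which count is intended is for the sponsor to state.
- State the arm and the denominator on which criterion 2 is judged (all participants randomised to CMT, if that is the intent).
- Report PiP attendance separately on its own 5-session scale.
- Report the number of CMT participants with exactly 5 sessions, so that the effect of the threshold is visible.

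This costs about two sentences of SAP wording and one extra line in the adherence table. No new data are needed, because session attendance is already being monitored. The downside is that the CMT percentage may look less favourable if the stricter count is kept.

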5.1 Primary outcome(s)

This research is a feasibility trial and therefore does not have a primary clinical outcome measure. The primary outcomes will therefore relate to the feasibility of conducting a future, fully powered RCT (recruitment, retention, and intervention adherence rates) and obtaining parameters required to inform its design and conduct, such as the standard deviation of outcome measures that may feed into the sample size calculation.

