10.4 Outcome data

Outcome data will be summarised descriptively by group (treatment vs control) and timepoint. We will plot line graphs to look at the trajectory of each outcome over time, looking at both individual participants and the mean values for each randomised group. As this is a feasibility study, no formal hypothesis testing will be undertaken to compare outcomes between the groups. Templates of the tables used to present outcome data can be viewed in Appendix (C). Potential clinical effectiveness will be considered by investigating the number of participants who experience a 30% improvement in pain/ function as measured by the Neck Disability Index at 6 months. We will also calculate the mean difference in the NDI score between the intervention and control groups, with a one-sided 80% and 90% confidence interval (CI) for this difference to see whether the interval includes the kind of difference that we would be looking for in the main trial. If, for instance, we saw a negative point estimate and our CI excluded say a 0.3 SD difference then this would be suggestive that it may not be worth moving forward to the main trial - at least with the intervention as tested in the feasibility study.

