Appendix C: Recruitment and retention summary tables

Table 2: Recruitment log

Site	Number Identified and sent PIS by CRN	Number contacted and screened (95% CI)	Number Consenting (95% CI)	Number Randomised (95% CI)	Number Withdrawn (95% CI)
Total					

Table 3: Withdrawal's log

Site	Participant ID	Reason for Withdrawal

Table 4: Summary of outcomes by treatment group and time point

Continuous outcome measures, N, mean (SD)	14 weeks			6 months		
	Intervention (n=x)	Control (n=x)	Overall (n=)	Intervention (n=x)	Control (n=x)	Overall (n=)
WOMAC Pain subscale						
PCS-H subscale						

PCS-M subscale						
PCS-R subscale						
PCS total score						
Tampa scale						
EQ-5D-5L index value score						
EQ-5D-5L VAS						
Categorical outcome measures, n (%)						
PCS total score ≥ 30						
Tampa scale >37						
Severe (20- 24)						

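### The outcome SD is a stated primary deliverable, but the SAP plans no pooled SD, no interval for it and no baseline-to-follow-up correlation

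*SAP*

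**What the plan says.** Section 5.1 states that there is no primary clinical outcome. The primary outcomes are feasibility rates and the parameters needed to design a full trial, "such as the standard deviation of outcome measures that may feed into the sample size calculation". Section 7 gives the size and its reason. "We plan to recruit 48 participants to the study", and "Assuming a dropout of 20%, this should provide approximately 19 in each group for the final analysis". It cites recommended sample sizes of 24 to 70 as sufficient "to provide a reliable estimate of parameters required to calculate the sample size for a main trial, e.g. standard deviation of continuous outcomes", and places 48 within that range.

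Section 10.5, headed as the primary analyses, covers the recruitment rate and the attrition rate, each with a 95% interval, and adherence. It does not mention the SD.

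Section 10.4 says "Outcome data will be summarised descriptively by group (treatment vs control) and timepoint". It adds individual and mean trajectory plots, a count of participants with a 30% improvement on the NDI, and the NDI mean difference "with a one-sided 80% and 90% confidence interval (CI) for this difference".

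The template for follow-up outcomes, Appendix C Table 4, shows N, mean and SD for each arm and overall at 14 weeks and 6 months. It has no row for the NDI, the NRS or the STarT MSK tool. Its first row is a WOMAC pain subscale, which is not among the outcomes listed in section 5.2.

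**The concern.** Of the quantities that section 5.1 names, the SD is the one that most directly sets the size of the next trial, and it has no planned estimator and no statement of precision. Two separate gaps follow.

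- **Imprecision of the SD.** Sample size is proportional to the variance, so error in the SD enters squared. A bare SD from about 38 people does not show the next design team how wide the plausible range is.
- **No correlation.** If the main trial adjusts for the baseline score, its residual variance is the raw variance times (1 − r²), where r is the baseline-to-follow-up correlation. Both scores are collected on the same participants, but only separate summaries at each time point are tabulated. Neither r nor the SD of the change score, from which r could be worked out, is planned.

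The table template adds a practical problem: followed literally, it would show no follow-up SD for the NDI or the NRS.

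**Working it through.** **Inputs from the SAP (section 7):** 48 recruited, 20% dropout, two arms.

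**The plan's own figure.** 48 × (1 − 0.20) = 38.4, or 19.2 per arm. The stated 19 per group is reproduced. The pooled within-arm SD then has 2 × 19 − 2 = 36 degrees of freedom.

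**Assumptions, not in the SAP:** normal outcomes; a main trial tested at two-sided 5% with 90% power; values of r as shown.

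**1. Interval for the SD.** With s the estimate and σ the true value, 36 s²/σ² follows a chi-square distribution on 36 degrees of freedom. The 95% limits for σ are s × √(36/χ²).
- Lower: √(36/54.44) = 0.81, squared 0.66.
- Upper: √(36/21.34) = 1.30, squared 1.69.

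The sample size that is truly needed therefore lies between 0.66 and 1.69 times the one computed from s.

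**2. Consequence for an unadjusted main trial sized on s.** The ratio of the sample size for 80% power to that for 90% power is [(1.960 + 0.842)/(1.960 + 1.282)]² = 0.747. True power is below 80% when s²/σ² < 0.747. That has probability P(χ²₃₆ < 26.9) = 0.136, about 14%.

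**3. Upper-limit sizing, as an illustration.** The one-sided 80% upper limit is s × √(36/28.73) = 1.12 s, and 1.12² gives N × 1.25. The 14% falls to about 3%.

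**4. The correlation.** Sizing on the raw SD and then adjusting for baseline makes the trial too large by 1/(1 − r²): 1.10 at r = 0.3, 1.33 at r = 0.5, 1.56 at r = 0.6.

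**5. Precision of r from this study.** At n = 38 and r = 0.5, Fisher's z is 0.549 with standard error 1/√35 = 0.169. The 95% interval is 0.21 to 0.71 after back-transformation. The factor 1 − r² then runs from 0.95 to 0.50.

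**6. The 'Overall' column.** With equal arms that differ by d SDs, the overall variance is about 1 + d²/4 times the within-arm variance: 1.02 at d = 0.3 and 1.06 at d = 0.5. This is small beside step 1.

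**The case against.** The SAP does not say that the main trial will be sized on the point SD. It says only that the SD may feed into the calculation, and the team that designs that trial can allow for uncertainty then. If the tables give N and SD by arm, anyone can compute the pooled SD and its chi-square interval by hand. The paired individual data will exist, so the correlation can be computed later. Section 10.4 does put intervals on the NDI contrast. The word 'reliable' in section 7 describes published recommendations and is not a claim about a particular result.

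Most of this stands, and it limits the point to an unplanned analysis of a named deliverable; nothing is irretrievably lost. It does not remove the point. The recruitment and attrition rates could equally be given intervals afterwards, yet the SAP plans those in advance. The correlation cannot be obtained from any planned table. The interval on the mean difference describes the treatment contrast and is not a statement of how well the SD is known. For the NDI and the NRS, the Table 4 template would not supply even the N and SD for a hand calculation.

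A reader might go further and infer that the main trial is more likely than not to be too small. The documents do not support that. For an unadjusted trial sized on the point SD, the chance that s falls below σ is P(χ²₃₆ < 36) = 53%, barely above even. With baseline adjustment the conclusion reverses once r exceeds about 0.14: the chance of falling below planned power is 38% at r = 0.3 and 14% at r = 0.5. The SAP also states no main-trial power against which a trial could be too small.

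**Conclusion.** The point holds as a gap between the stated outcomes and the planned analysis. The SD belongs to the primary outcomes and to the sample-size rationale, but the primary analyses contain no pooled within-arm estimate, no interval and no baseline-to-follow-up correlation.

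The harm is imprecision that goes unreported, not a systematic bias towards too small a trial. The sample size could be off by a factor of 0.66 to 1.69, and there is a 14% chance that an unadjusted trial planned at 90% power would have less than 80%. The missing correlation acts in the other direction and should be kept apart: it would oversize an adjusted trial, by 1.33 at r = 0.5. The figures rest on 19 completers per arm, normality, two-sided 5% testing, and assumed values of power and r. The NDI and NRS are bounded scales, so the chi-square limits are approximate.

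The missing rows and the stray WOMAC row in Appendix C Table 4 need no assumptions; they conflict directly with sections 5.2 and 10.4. The point is worth correcting before analysis, but it does not threaten the trial.

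**What to change.** Add to section 10.5, for the NDI and the NRS at 14 weeks and 6 months:

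- the pooled within-arm SD with a two-sided 95% interval, with a bootstrap interval as a check because the scales are bounded;
- the pooled within-arm correlation of baseline with follow-up, with a 95% interval.

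State that the main-trial sample size will be shown across these limits and not from the point SD or the 'Overall' SD alone. Showing it also at the one-sided 80% upper limit of the SD is one reasonable convention, but it need not bind the main trial. Because r will itself be imprecise, show the adjusted sample size over its interval too.

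In Appendix C Table 4, add rows for the NDI, the NRS and the STarT MSK tool, and remove the WOMAC pain subscale.

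The cost is a few lines of SAP text and a short analysis of data already being collected. The downside is that the sample size shown at the 80% upper limit is about 25% larger than at the point SD, partly offset where baseline adjustment is used.
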